- **B.** RESEARCH PROCEDURES INVOLVED. Provide a short description of sequence and methods of procedures that will be performed with human subjects. Include details of painful or uncomfortable procedures, frequency of procedures, time involved, names of psychological tests, questionnaires, restrictions on usual life patterns, and follow up procedures.

Objective: Employ a mixed-methods study design with three complementary research components in this pilot feasibility study to examine the Y-T program implementation process in school communities (Aim 1), understand participant experience and engagement with the Y-T program (Aim 2), and the impact of the Y-T iCBT intervention designed for adolescents to address depression and anxiety symptomology and addictive behaviors (Aim 3). As part of this pilot feasibility study, we will track institutional processes, policies, and obstacles that impact the implementation and evaluation of the Y-T program. These data will inform the future dissemination, collaboration and implementation of such interventions in school settings. We will conduct several focus groups to ascertain the acceptability and user engagement experience to understand the qualitative experience of the iCBT intervention with youth participants. We will provide access to the iCBT intervention and collect self-report data on outcomes of depression and anxiety (**Beck's Youth Inventories- Second Edition**), and substance use behaviors (**Adolescent Substance Abuse Subtle Screening Inventory**) at baseline and 4, 8, 12, and 16-week time periods at two separate school sites. The proposed research design is a 4- to 16-week waitlist control group model.

- **Dependent variable(s):** School Community implementation process, participants' experience of and engagement with Y-T program, and behavioral trends of participants' experience of depressive and anxiety symptomology and addictive behaviors/attitudes
- **Independent Variable**: Implementation process in school community, and participation in online Y-T iCBT program which teaches skills pertaining to wellbeing, depressive and anxiety symptomology, coping strategies and addictive behaviors.

Intervention: iCBT Youth Thrive (Y-T) program

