Qualitative Data (Aim 2). We will conduct several qualitative focus groups with randomly selected youth participants at both sites to ascertain the acceptability and user engagement experience to understand the qualitative experience of the Y-T intervention. We utilize best practice in conducting online focus groups and will develop an open-ended focus group guide and facilitate a number of distance (via Webex or Zoom) focus groups at each of the study administration sites. Focus groups will be audio-recorded and transcribed for analysis. Questions will examine acceptability, program engagement, and qualitative experiences of using the program. Participants will include a subset of the quantitative study phase (see focus group guide). Two- three focus groups will be conducted at each research site, and last 30 minutes to an hour.

Quantitative Data (Aim 3). We will also engage a preliminary group (school)-randomized waitlist-control group study design with the two identified sites to collect self-report data on outcomes of depression, anxiety, and substance use behaviors at baseline, 3-week, 6-week, and 8-week time periods (4 times over an 8-week intervention period). The MSU research team will orient school staff to the behavioral health assessment tools used in study, and school community protocols identified should participant safety issues emerge. It is important to note that we have explored the potential for a randomized waitlist controlled study design, and our school community partners have expressed some concern that it would be difficult to initially implement this type of design. In the event that we are unable to perform a WLC design, then we will evaluate baseline, 3-, 6- and 8-week outcomes only with no group comparisons.

Analysis Plan.

Process Analysis (Aim 1). At the end of study implementation, the research team will meet to discuss and summarize all process data that are collected; we will also conduct monthly meetings with key school personnel.

Qualitative Analysis (Aim 2). We will conduct content analysis on each of the focus group transcripts, using multiple coders for verification and consensus-building.

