Quantitative Analysis (Aim 3). Analyses will be conducted using SAS or SPSS statistical software using a mixed-model ANCOVA, with regression adjustment for the baseline depression scores for both the primary outcome measures using the BYI-2 and the secondary outcome measures form the Adolescent Substance Abuse Subtle Screening Inventory (SASSI-A2). The intent of this analysis is to understand the effects of the iCBT intervention on each outcome measure (anxiety, depression, and substance use/abuse), and to explore differences by participant characteristics.

Baseline and Intervention Phase Quantitative Assessment Measures:

- Beck's Youth Inventories- Second Edition (BYI-2): The BYI-2 measures symptoms/experiences of
 depression, anxiety, anger, self-concept, and disruptive behavior. The BYI-2 aligns with co-occurring
 symptom criteria specific to anxiety and depression from the Diagnostic and Statistical Manual of
 Mental Disorders (DSM-IV-TR). This assessment takes about 10 minutes to administer.
- SASSI-A2 (Adolescent Substance Abuse Subtle Screening Inventory): The SASSI-A2 helps identify the probability of substance dependence and substance abuse disorders in adolescents and provides clinical insight into family and social risk factors, level of defensive responding, and consequences of substance misuse. The SASSI-A2 aligns with diagnostic symptom criteria specific to addiction and substance use disorders from the DSM-IV-TR. This assessment takes approximately five minutes to administer.

The evaluation team (Drs. [name] and [name], CAIRHE staff) will review all data results in sensitive timeframes. [name], Principal Investigator of the evaluation, will work closely with MSU's Office of Sponsored Programs and IRB to ensure the safety and confidentiality of research participants, and ensure responsible conduct of research.

The Standards for Educational and Psychological Testing published by the American Educational Research Association (AERA), American Psychological Association (APA), and the National Council on Measurement in Education (NCME) maintain strict qualification regulations for assessment administration. A central principle of professional test use is that individuals should use only those tests for which they have the appropriate training and expertise (classifications A-C). [name] is an approved classification "C", the highest level of test administration classification.

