C. DECEPTION – At no point will deception be used in this study. The fore-mentioned Youth-Thrive program is designed to increase adaptive coping strategies in wellbeing and behavioral health, and the youth participants (and their guardians) will be informed of that.

D. SUBJECTS

1. Approximate number and ages How Many Subjects: **100**

Age Range of Subjects: 13 -18 years old

How Many Normal/Control: 50

Age Range of Normal/Control: 13- 18 years old

- 2. Criteria for selection: Participants are enrolled in Montana Public Education at either Park County **High** School in Gardiner, Montana or Custer County High School in Miles City, Montana. Youth participants will be currently enrolled in a Health Enhancement class where Youth Thrive will be implemented and delivered as part of the Health Enhancement education curriculum.
- 3. Criteria for exclusion: N/A; lack of parental/guardian consent and/or participant assent for participation in research study.
- 4. Source of Subjects (including patients): Existing, enrolled students at Park County and Custer County (Miles City) High Schools. Please see included letters of support from school districts.
- 5. Who will approach subjects and how? Explain steps taken to avoid coercion. School officials will be initial point of content regarding participation in the research study. As part of the informed consent process, parents/guardians will have option to opt out on behalf of their minor in terms of participation in the research aspect of the Youth Thrive program delivery. Additionally, students will be provided an informed consent and provide their assent to participation as well.
- 6. Will subjects receive payments, service without charge, or extra course credit? **Yes** or No (If yes, what amount and how? Are there other ways to receive similar benefits?) The Y-T program will be delivered as part of the Health Enhancement course, students will receive participation grades and credit in the high school course needed for graduation. Additionally, students are eligible to receive a \$50 gift card to Amazon if they complete all research assessments (BYI-2 and SASSI) and, if randomly selected **to** participate in focus groups.

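### With two schools randomised, each arm is one school, so the Aim 3 ANCOVA cannot separate a Youth Thrive effect from a school difference

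*Combined protocol and SAP*

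**What the plan says.** Under Data Collection, Quantitative Data (Aim 3), the protocol proposes a "preliminary group (school)-randomized waitlist-control group study design with the two identified sites". Section D, item 1, gives 100 subjects and "How Many Normal/Control: 50". The same Aim 3 paragraph reports that the school partners doubt the design can be implemented. It adds a fallback: if the team is "unable to perform a WLC design, then we will evaluate baseline, 3-, 6- and 8-week outcomes only with no group comparisons".

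The Analysis Plan for Aim 3 specifies a mixed-model ANCOVA "with regression adjustment for the baseline depression scores for both the primary outcome measures using the BYI-2 and the secondary outcome measures". It names no school term, no contrast within the waiting school before and after it starts the program, and no limit on interpretation. On purpose it says: "The intent of this analysis is to understand the effects of the iCBT intervention on each outcome measure". The opening statement of purpose lists efficacy among the things to be examined, and research question 3 asks about the program's impact on symptoms and substance use.

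Two assessment schedules appear. The Objective in Section B places assessments "at baseline and 4, 8, 12, and 16-week time periods at two separate school sites" and adds: "The proposed research design is a 4- to 16-week waitlist control group model". The Aim 3 paragraph gives "baseline, 3-week, 6-week, and 8-week time periods (4 times over an 8-week intervention period". The two share only baseline and week 8.

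**The concern.** Allocating two schools to two arms makes arm and school the same variable. Anything that differs between the schools and is not carried by the baseline depression score is then counted as a program effect. That includes a teacher, a local event, a seasonal pattern or a difference in delivery during follow-up. Baseline adjustment cannot remove something that happens after baseline. The plan does track school policies and events under Aim 1. That helps interpretation, but it is not statistical control.

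If the comparison is run and analysed as written, a difference between two particular schools could be reported as efficacy or impact, although the design supports only a description of those two schools. A secondary problem is that anxiety and the SASSI-A2 are adjusted for baseline depression rather than for their own baselines, so part of any school difference in those baselines is left in the comparison.

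**Working it through.** The documents state no alpha, power, ICC, standard deviation or target effect, so there is no figure of the plan's own to reproduce. The inputs taken from them are two schools, school as the unit of allocation, 50 controls of 100 (hence about 50 per school), and baseline depression as the only named covariate. The Park County town differs between Study Population and Section D, item 2, but the number of sites is two throughout. Everything else below is an assumption and is marked as one.

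**1. Structure (no assumed input).** Between-school degrees of freedom = schools − arm means = 2 − 2 = 0. The arm and school indicator columns are identical: a design matrix with intercept, arm and school has rank 2, the same as without arm. A random school effect, if the term mixed-model was meant to include one, has no degrees of freedom from which to be estimated separately from arm.

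**2. Type I error if school is ignored (illustration).** Assumptions: two-sided 5%, 50 students per school, one follow-up, no true effect, and ICC defined as the school share of the variance left after baseline adjustment. The true variance of the arm difference, relative to the variance the model assumes, is

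VR = [ICC + (1 − ICC)/50] / [(1 − ICC)/50],

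and the type I error is 2 × [1 − Φ(1.985/√VR)].

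| ICC | VR | Type I error, formula | Type I error, simulated ANCOVA (20,000 runs) |
|---|---|---|---|
| 0 | 1.000 | 0.047 | 0.051 |
| 0.01 | 1.505 | 0.106 | 0.107 |
| 0.02 | 2.020 | 0.163 | 0.162 |
| 0.05 | 3.632 | 0.298 | 0.294 |

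If the ICC is instead a share of total variance, with an assumed baseline-to-follow-up correlation of 0.6, then ICC 0.01 / 0.02 / 0.05 gives 0.138 / 0.218 / 0.380. VR can be rewritten as 1 + 50 × ICC/(1 − ICC). The number of students per school multiplies the ICC term, so a larger sample makes the error worse.

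**3. The same point without treating schools as random draws.** Suppose the two schools differ by a fixed d residual SDs and the program has no effect. The standard error of the difference is √(2/50) = 0.2, and the chance of a significant result is Φ(d/0.2 − 1.96) + Φ(−d/0.2 − 1.96). For d = 0.1 / 0.2 / 0.3 / 0.5 this is 0.079 / 0.170 / 0.323 / 0.705.

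**4. Depression as the covariate for other outcomes (illustration).** Let d be the school difference in baseline anxiety, dD the school difference in baseline depression, rho the anxiety-depression correlation, and r the correlation of anxiety from baseline to follow-up. The false difference left after adjusting for depression is r × (d − rho × dD). With assumed d = 0.3 SD and r = 0.6:

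- dD = 0: 0.6 × 0.3 = 0.180 SD.
- dD = 0.15, rho 0.5 / 0.7: 0.6 × (0.3 − 0.075) = 0.135 SD; 0.6 × (0.3 − 0.105) = 0.117 SD.
- dD = 0.3, rho 0.5 / 0.7: 0.6 × (0.3 − 0.15) = 0.090 SD; 0.6 × (0.3 − 0.21) = 0.054 SD.

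Adjusting for anxiety's own baseline brings this to about 0 in a linear model without measurement error.

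**5. Data from the waiting school after it starts.** Counting assessments strictly later than an assumed wait of 4 / 8 / 12 / 16 weeks, with both schools on one calendar from a common baseline, leaves 3 / 2 / 1 / 0 under the Objective's schedule and 2 / 0 / 0 / 0 under the Aim 3 schedule.

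**The case against.** The strongest reply is that the data are longitudinal. A model with school, assessment time and a time-varying exposure indicator, taking baseline as an outcome row, has full rank on both schedules for waits of 4, 8, 12 and 16 weeks. Stable school differences could then be separated from exposure. That is correct as far as it goes, but it is not the planned analysis, and it requires that the two schools would have followed parallel courses over time. Two schools cannot test that assumption. In an ANCOVA, where only follow-up scores are outcomes, exposure is still aliased with school for waits of 8 weeks or more on the Aim 3 schedule and for a 16-week wait on the Objective's schedule.

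The plan is also tentative. It calls itself a pilot, speaks of trends, labels the design preliminary and provides a fallback without group comparison. Aims 1 and 2 are untouched. All of this limits the consequence. However, the fallback applies only if the waitlist design cannot be run, and the problem arises when it is.

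Three smaller points stand. The impact sentence under Research Design describes pre- and post-assessments, not a between-school contrast, so the evidence of intent rests mainly on the Aim 3 Analysis Plan and the efficacy wording. The Aim 3 schedule could be read as running from each school's own start, in which case the waiting school would have three assessments after starting whatever the wait. And the error rates rest on assumed inputs apart from the 50 per arm.

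**Conclusion.** The concern holds, conditional on the school-randomised waitlist design being run with two schools. The certain part is structural: one school per arm, 0 between-school degrees of freedom, and no remedy in the planned ANCOVA for school-specific trends or events. The type I error figures (about 11% to 30% for a residual ICC of 0.01 to 0.05) and the leftover differences of 0.05 to 0.18 SD in anxiety are illustrations under stated assumptions, not estimates for these schools. Whether usable data would exist from the waiting school after it starts cannot be settled, because the two schedules conflict and the length of the wait is not fixed. This should be corrected before the Aim 3 comparison is analysed; it does not affect the feasibility and qualitative aims.

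**What to change.** In the Aim 3 data-collection and analysis paragraphs, state that under whole-school allocation the between-school contrast is descriptive: means, differences and within-school change, by school, with no p-value and no claim that it estimates the program's effect. Use each outcome's own baseline in any adjusted summary. Align the efficacy wording in the opening statement and the impact wording in research question 3 and Research Design with this.

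Reconcile the assessment schedules in the Objective and the Aim 3 paragraph. State the length of the wait and whether assessments run from a common date or from each school's own start.

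The analysis and wording changes are text only, and the baselines are already collected. Reconciling the schedules may change what is collected, depending on what the team decides. The real cost is a weaker claim: the pilot could not report a tested effect from the school comparison. If a tested effect is wanted, more and smaller units, such as class sections, would have to be randomised. That is a larger design change, and the school partners already have doubts about randomised allocation.

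### The Aim 3 ANCOVA adjusts every outcome for baseline depression, so anxiety and SASSI-A2 are not adjusted for their own baselines, which are collected

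*Combined protocol and SAP*

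**What the plan says.** Under Analysis Plan, Quantitative Analysis (Aim 3), the model is named as an ANCOVA of mixed-model type, to be fitted in SAS or SPSS. The covariate is then specified: "with regression adjustment for the baseline depression scores for both the primary outcome measures using the BYI-2 and the secondary outcome measures". The secondary measures are those of the SASSI-A2. Baseline depression is the only covariate named, and it is tied explicitly to both instruments. The same paragraph gives the purpose as to "understand the effects of the iCBT intervention on each outcome measure (anxiety, depression, and substance use/abuse").

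Under Data Collection, Quantitative Data (Aim 3), the study will "collect self-report data on outcomes of depression, anxiety, and substance use behaviors at baseline, 3-week, 6-week, and 8-week time periods". The Objective paragraph of section B gives a different follow-up schedule, "at baseline and 4, 8, 12, and 16-week time periods at two separate school sites", but it too includes baseline. On either schedule the baseline anxiety and substance-use values will exist.

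The comparison these covariates would serve is a "preliminary group (school)-randomized waitlist-control group study design with the two identified sites". If that proves impracticable, "then we will evaluate baseline, 3-, 6- and 8-week outcomes only with no group comparisons".

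The plan gives no model equation, no random effects, and no statement of whether baseline is a covariate or one of the repeated responses.

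**The concern.** In an ANCOVA the baseline of the outcome being analysed is usually its strongest available predictor. Adjusting for it narrows the interval and corrects the estimate for whatever difference in that outcome the groups had at the start. Baseline depression does this well for depression, partly for anxiety, and probably weakly for substance use.

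An analyst who followed the text literally would fit baseline depression in the anxiety and SASSI-A2 models and leave those outcomes' own baselines unused. Anxiety is one of the BYI-2 outcomes, which the plan labels primary, so the gap is not confined to a secondary measure. With only two intact schools, a starting difference in anxiety or substance use is plausible, and recruiting more students would not reliably remove it.

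**Working it through.** The plan states no standard deviation, correlation, effect size, alpha or power for Aim 3, so it has no figure to reproduce. What follows sizes the issue under declared assumptions.

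**From the documents.** About 100 students, 50 of them controls (section D, item 1), so 100 − 50 = 50 in the other arm; two schools, one per arm.

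**Assumed, not in the documents.** Outcomes are standardised and continuous, and students are independent. The correlation of an outcome's own baseline with its follow-up (*own*) is 0.6 to 0.7. The correlation of baseline depression with that follow-up (*cross*) is 0.4 to 0.5 for anxiety and 0.2 to 0.3 for substance use.

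**1. Precision.** Residual variance is 1 − cross² with depression-only adjustment and 1 − own² with own-baseline adjustment.

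SE ratio = √[(1 − cross²) / (1 − own²)]

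| | cross 0.5 | cross 0.4 | cross 0.3 | cross 0.2 |
|---|---|---|---|---|
| own 0.6 | 1.08 | 1.15 | 1.19 | 1.22 |
| own 0.7 | 1.21 | 1.28 | 1.34 | 1.37 |

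For example, √(0.84/0.64) = 1.15 and √(0.96/0.51) = 1.37. The standard error is therefore about 8% to 28% larger for anxiety and 19% to 37% larger for substance use.

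**2. Baseline difference left in the estimate.** Let dA be the between-school difference in the outcome's own baseline, dD the difference in baseline depression, and rbb the correlation between the two baselines.

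- Depression-only adjustment leaves bA × (dA − rbb × dD), with bA = (own − cross × rbb)/(1 − rbb²).
- Own-baseline adjustment leaves bD × (dD − rbb × dA), with bD = (cross − own × rbb)/(1 − rbb²).

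Take own 0.6, cross 0.4, rbb 0.6 and dA = 0.3 SD. Then bA = 0.36/0.64 = 0.5625 and bD = 0.04/0.64 = 0.0625.

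| Case | Depression-only | Own baseline |
|---|---|---|
| Depression balanced, dD = 0 | 0.5625 × 0.3 = 0.169 SD | 0.0625 × (−0.18) = −0.011 SD |
| Depression moves along, dD = 0.6 × 0.3 = 0.18 | 0.5625 × (0.3 − 0.108) = 0.108 SD | 0.0625 × (0.18 − 0.18) = 0 |

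With own at 0.6 to 0.7 and dA = 0.3 SD, the amount left by depression-only adjustment is:

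- anxiety (cross 0.4–0.5, rbb 0.5–0.7): 0.14–0.25 SD if depression is balanced, 0.08–0.15 SD if it moves along;
- substance use (cross 0.2–0.3, rbb 0.2–0.4): 0.17–0.22 SD and 0.14–0.20 SD.

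**3. Simulation.** With 50 independent students per arm and 8,000 runs, the worked case left 0.168 and 0.106 SD under depression-only adjustment, against −0.011 and −0.003 SD with the own baseline. Simulated SE ratios were 1.13–1.14 (formula 1.15), 1.08 for own 0.6/cross 0.5 (formula 1.08) and 1.39 for own 0.7/cross 0.2 (formula 1.37).

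**4. A second set of assumptions.** Let own be 0.5–0.7 and cross = own × rbb, with rbb 0.5–0.7 for anxiety and 0.1–0.4 for SASSI-A2. Adding the own baseline cuts residual variance to 0.58–0.85 of the depression-only value for anxiety and 0.51–0.78 for SASSI-A2. At own = rbb = 0.6 the ratio is 0.64/0.8704 = 0.74, and with 50 per arm the SE falls from √(2 × 0.8704/50) = 0.187 to √(2 × 0.64/50) = 0.160 SD. A 0.3 SD difference that depression moves with leaves 0.08–0.16 SD (anxiety) or 0.13–0.21 SD (SASSI-A2). The direction was the same at every value in this grid.

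**The case against.** **The plan does not say *only*.** The wording may be loose drafting for each outcome's own baseline score, and a mixed model could carry baseline as a repeated response, in which case own baselines would enter. Both readings are possible, but the plan states neither. The one covariate it names is applied expressly to both instruments, and the same correction is needed whichever was meant.

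**The precision figures assume independent students.** This stands as a limit on size. With one school per arm there are 2 − 2 = 0 degrees of freedom between schools, so a student-level interval is already too narrow. Suppose a between-school residual variance τ that is the same under both adjustments; the SE ratio becomes √[(τ + (1 − cross²)/50)/(τ + (1 − own²)/50)]. For own 0.6/cross 0.4, the 15% becomes √(0.0268/0.0228), or 8%, at τ = 0.01 and √(0.0668/0.0628), or 3%, at τ = 0.05. The 37% extreme becomes about 20%, 7% and 4% at τ = 0.01, 0.05 and 0.10. If the own baseline also explained part of the school difference, the gain would be larger than these figures. This argument does not remove the leftover baseline difference in step 2.

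**The range depends on the inputs.** True: with own at 0.5 the SE formula gives only 6% at cross 0.4 and 0% at cross 0.5. The plan also does not say which SASSI-A2 score is analysed, so treating it as continuous is a further assumption. Both affect the illustrated size rather than the remedy.

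**It is a pilot, and the comparison may not happen.** There is no power target to miss, and depression is handled correctly. Under the fallback the issue does not arise. But the waitlist comparison is the stated plan, and Aim 3 sets out to estimate an effect on each outcome.

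**Conclusion.** The concern holds. As written, the plan adjusts anxiety and SASSI-A2 outcomes for baseline depression and not for their own baselines, which are collected. If the waitlist comparison is run, the cost is a student-level SE about 8% to 37% larger over the assumed correlations, less once school clustering is allowed for. In the worked case, about 0.11 to 0.17 SD of a 0.3 SD baseline difference also stays in the estimate.

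That leftover is imbalance in the trial as realised, not bias averaged over the random allocation of schools. Own-baseline adjustment does not cure the complete confounding of arm with school, which is a separate limit. Confidence is high on the text and the direction; the size rests on assumed correlations. The sponsor should make the change, though the defect does not invalidate the study.

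**What to change.** Replace the covariate wording in Quantitative Analysis (Aim 3) with text to this effect:

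> Each outcome will be adjusted for the baseline value of that same outcome (BYI-2 depression for depression, BYI-2 anxiety for anxiety, SASSI-A2 score for SASSI-A2), with the post-baseline visits as the response. Baseline depression may be included as an additional covariate. This adjustment applies to the waitlist comparison and does not separate the intervention effect from a difference between schools.

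Name the SASSI-A2 score to be analysed in the same place. If the intention was instead to model baseline as a repeated response, say so and give the model. The cost is one or two sentences; no new data, visits or burden on students are involved.
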